2.8.1 Adverse events (AEs)

For adverse events and other binary safety variables crude incidence and exposure time-adjusted incidence will be derived as described below and summarized in [Table 2-8](#).

All adverse events are summarized based on treatment emergent only. The definition for “treatment emergent” is as below:

- events started after the first dose of study medication or events present prior to the first dose of study medication but increased in severity based on preferred term
- and started prior to the last dose plus 84 days (inclusive)

All adverse events will be listed with “treatment emergent” flag displayed.

Table 2-8 Overview of analyses on some safety endpoints

Analysis period	AEs & SPP/RMP risks	SAEs	AEs-SMQ	AEs by severity	study treatment related AEs, death & other significant AEs	notables (lab/vitals)
treatment period 1 (up to week 12)	•crude incidence	•crude incidence				
Entire treatment period (including all data)	•crude incidence •exp.time adjusted incidence*	•crude incidence	•crude incidence			

*Note, Exposure adjusted incidence rates will be provided and follow the guideline as below:

- Primary SOC level for AE and SAE
- Level 1 for risks and SMQ
- PT level for SAE
- PT level for AE $\geq 2\%$ or incidence rate per 100 subject years ≥ 5.0 in any treatment group
- Other selected AEs of special interest on lower levels (e.g. PT or SMQ level 2), if appropriate

The crude incidence of treatment emergent adverse events will be presented for the treatment period up to Week 16 LPLV for W16 primary analysis, and treatment period including all data for final analysis. The crude incidence of treatment emergent adverse events will be summarized by primary System Organ Class (SOC) and Preferred Term (PT). Confidence intervals for the crude rate will be derived using the score method including continuity correction (Newcombe 1998) as described in [Section 5.4.5](#). In addition, exposure time-adjusted incidence rates will be provided for the treatment period including all data (see [Section 5.4.6](#)).

Adverse events will be summarized by presenting, for each treatment group, the number and percentage of subjects having at least one AE, having an AE in each primary system organ class and having each individual AE (preferred term). Summaries will also be presented for AEs by severity and for study treatment related AEs. If a particular AE ‘severity’ is missing, this variable will be listed as missing and treated as missing in summaries. If a subject reported more than one adverse event with the same preferred term, the adverse event with the greatest severity will be presented. If a subject reported more than one adverse event within the same primary system organ class, the subject will be counted only once with the greatest severity at the system organ class level, where applicable.

Adverse events will also be reported separately by standardized or customized MedDRA queries (SMQ or CMQ/NMQ). The MedDRA version used for reporting the adverse events will be described in a footnote.

The most common adverse events reported ($\geq z\%$ in any group for each preferred term in the table by SOC and PT or $\geq z\%$ in any group for each grouping term table) will be presented in descending frequency according to its incidence in secukinumab group starting from the most common event. Here threshold value z is set to 2 (%) but it may be updated following review of the dry run outputs.

A graphical display of the crude rates or exposure adjusted incidence rates within system organ classes will be presented as follows: For all AEs regardless of severity and seriousness, the point estimate within system organ classes will be presented graphically with system organ class on the y-axis. This figure will consist of two panels: i) point estimate of AEs, ii) point estimate of serious AEs. For the exposure adjusted incidences a linear-scale will be used on the x-axes. Separate summaries will be provided for deaths, serious adverse events, other significant adverse events leading to discontinuation and adverse events leading to dose adjustment or interruption.

Algorithms for date imputations will be provided in [Section 5](#).

Other safety topics of interest, such as risks defined in the Safety Profiling Plan, Risk Management Plan or topics of interest regarding signal detection or routine analysis are defined in the Program Case Retrieval Sheet that is stored in [REDACTED]

Crude rate of important identified and potential risks from Case Retrieval Sheet will be provided for all (non-serious and serious) cases and for all serious cases. Exposure-time adjusted rates will be provided for treatment period including all data for all (non-serious and serious) cases and for all serious cases. In addition, listings will be provided for the related AE risks.

Risk measures and confidence intervals will be derived according to [Section 5](#).

The version of the Case Retrieval Sheet used for the analyses will be described in a footnote. This includes MedDRA version and Novartis MedDRA Query (NMQ) dictionary date.

A separate table of injection site reaction related AEs caused by the 2 mL AI and the 1 mL PFS respectively will be provided. Additional analyses on the severity, outcome, etc. of the AEs caused by AI and PFS respectively may be performed to support health authority interactions as necessary.

Important note: For the evaluation of risks primary and secondary system organ classes of the MedDRA dictionary will be considered.

For the legal requirements of ClinicalTrials.gov and EudraCT, two required tables on adverse events which are not serious adverse events (PT) with an incidence greater than >2% and on SAEs suspected to be related to study treatment will be provided by system organ class and preferred term on the safety set population.

If for a same patient, several consecutive AEs (irrespective of study treatment causality, seriousness and severity) occurred with the same SOC and PT:

- a single occurrence will be counted if there is ≤ 1 day gap between the end date of the preceding AE and the start date of the consecutive AE

- more than one occurrence will be counted if there is > 1 day gap between the end date of the preceding AE and the start date of the consecutive AE

For occurrence, the presence of at least one SAE / SAE suspected to be related to study treatment / non SAE has to be checked in a block e.g., among AE's in a ≤ 1 day gap block, if at least one SAE is occurring, then one occurrence is calculated for that SAE.

The number of deaths resulting from SAEs suspected to be related to study treatment and SAEs irrespective of study treatment relationship will be provided by SOC and PT.

2.8.2 Deaths

Separate summary and listing will be provided for deaths.

2.8.3 Laboratory data

The summary of laboratory evaluations will be presented for two groups of laboratory tests (hematology and serum chemistry).

Descriptive summary statistics for the change from baseline to each study visit will be presented by laboratory test and treatment group. Change from baseline will only be summarized for subjects with both baseline and post baseline values and will be calculated as:

$$\text{change from baseline} = \text{post baseline value} - \text{baseline value}$$

Only "on-treatment" laboratory data will be summarized (i.e. assessments within last dose plus 84 days). All laboratory data will be listed with "on-treatment" flag displayed. If two measurements are taken on the same date/time/CRF visit then use the average of two assessments.

For laboratory test values below Lower Level of Quantification (LLQ) or above Upper Level of Quantification (ULQ) will be imputed as LLQ or ULQ value, respectively. The numerical part of the reported result will be treated as the actual LLQ or ULQ. These laboratory values will be displayed in listings using the standard unit with the reported sign ("<" or ">"). For example, the actual lab result is "<5" and LLQ = 10, it will be reported for the numerical part as 5 and listed as "<5", LLQ will be imputed as 5.

In addition, shift tables may be provided as required at ad-hoc basis for all parameters to compare a subject's baseline laboratory evaluation relative to the most extreme laboratory test value within a treatment period. For the shift tables, the normal laboratory ranges will be used to evaluate whether a particular laboratory test value is normal, low, or high (including category "high and low"). These summaries will be presented by laboratory test and treatment group. Subjects with abnormal laboratory values will be listed and values outside the normal ranges will be flagged.

The following laboratory parameters will be analyzed with respect to numerical Common Terminology Criteria for Adverse Events (CTCAE) grades, given in [Table 2-9](#): hemoglobin, platelets, white blood cell count, neutrophils, lymphocytes, creatinine, total bilirubin (TBL), gamma-glutamyl transferase (GGT), alanine aminotransferase (ALT), aspartate aminotransferase (AST), alkaline phosphatase (ALP).

The number and percentage of subjects with CTCAE grade newly occurring or worsening after baseline will be presented. These summaries will be split into hematology and chemistry.

Table 2-9 CTCAE grades for laboratory parameters to be analyzed

CTCAE v4.0 Term	Grade 1	Grade 2	Grade 3	Grade 4
HGB decreased (Anemia)	<LLN – 100 g/L	<100 – 80 g/L	<80 g/L	Life-threatening consequences; urgent intervention
Platelet count decreased	<LLN – 75.0 x10e9 /L	<75.0 - 50.0 x10e9 /L	<50.0 – 25.0 x10e9 /L	<25.0 x 10e9 /L
White blood cell decreased	<LLN - 3.0 x 10e9 /L	<3.0 - 2.0 x 10e9 /L	<2.0 - 1.0 x 10e9 /L	<1.0 x 10e9 /L
Neutrophil count decreased	<LLN - 1.5 x 10e9 /L	<1.5 - 1.0 x 10e9 /L	<1.0 - 0.5 x 10e9 /L	<0.5 x 10e9 /L
Lymphocyte count decreased	<LLN - 0.8 x 10e9/L	<0.8 - 0.5 x 10e9 /L	<0.5 - 0.2 x 10e9 /L	<0.2 x 10e9 /L
Creatinine increased	>ULN - 1.5 x ULN	>1.5 - 3.0 x ULN	>3.0 - 6.0 x ULN	>6.0 x ULN
TBL increased	>ULN - 1.5 x ULN	>1.5 - 3.0 x ULN	>3.0 - 10.0 x ULN	>10.0 x ULN
GGT increased	>ULN - 2.5 x ULN	>2.5 - 5.0 x ULN	>5.0 - 20.0 x ULN	>20.0 x ULN
ALT increased	>ULN - 3.0 x ULN	>3.0 - 5.0 x ULN	>5.0 - 20.0 x ULN	>20.0 x ULN
AST increased	>ULN - 3.0 x ULN	>3.0 - 5.0 x ULN	>5.0 - 20.0 x ULN	>20.0 x ULN
ALP increased	>ULN - 2.5 x ULN	>2.5 - 5.0 x ULN	>5.0 - 20.0 x ULN	>20.0 x ULN

Shift tables will be presented comparing baseline laboratory result (CTCAE grade) with the worst results (expressed in CTCAE grade) during the treatment phase analyzed. Of note, baseline will be defined as last assessment prior to first dosing in initial treatment phase. If no pre-treatment value exists, also a value recorded after first dose can be used as baseline if it was collected on the same day as first dose, see [Section 2.1.1.3](#).

Exposure time adjusted incidence for subjects with newly occurring neutropenia of CTCAE grade ≥ 2 will be summarized

The number and percentage of subjects with newly occurring liver enzyme abnormalities will also be summarized based on the event criteria given in [Table 2-10](#).

Table 2-10 Liver-related events

Parameter	Criterion
ALT	>3xULN; >5xULN; >8xULN; >10xULN, >20xULN
AST	>3xULN; >5xULN; >8xULN; >10xULN; >20xULN
ALT or AST	>3xULN; >5xULN; >8xULN; >10xULN; >20xULN ALT or AST >3xULN & (nausea or vomiting or fatigue or general malaise or abdominal pain or (rash and eosinophilia))
TBL	>1xULN; >1.5xULN; >2xULN; >3xULN,
ALP	>1.5xULN; >2xULN; >3xULN; >5xULN
ALT or AST & TBL	ALT or AST >3xULN & TBL >1.5xULN; ALT or AST >3xULN & TBL >2xULN; ALT or AST >5xULN & TBL >2xULN; ALT or AST >8xULN & TBL >2xULN; ALT or AST >10xULN & TBL >2xULN; ALT or AST >20xULN & TBL >2xULN;
ALP & TBL	ALP >3xULN & TBL >2xULN ALP >5xULN & TBL >2xULN
ALT or AST & TBL & ALP	ALT or AST >3xULN & TBL >2xULN & ALP <2xULN (Potential Hy's Law) Note: elevated ALP may suggest obstruction as a consequence of gall bladder or bile duct disease; ALP may also be increased in malignancy. FDA therefore terms Hy's Law cases as indicators of pure hepatocellular injury . This does not mean that cases of ALT or AST >3xULN & TBL >2xULN & ALP \geq 2xULN may not result in severe DILI. ALT or AST >3xULN & TBL >2xULN & ALP <2xULN (Potential Hy's Law) or reported Hy's Law case Note: "Hy's Law case" is a lower level term in MedDRA (10070546) and may be reported as AE.

For a combined criterion to be fulfilled, all conditions have to be fulfilled on the same visit. The criteria are not mutually exclusive, e.g., a subject with ALT = 6.42xULN is counted for ALT >3xULN and ALT >5xULN.

Individual subject data listings will be provided for subjects with newly occurring or worsening abnormal laboratory data. Data of subjects with newly occurring liver enzyme abnormalities will be listed in an additional listing.

Fasting laboratory tests including fasting plasma glucose and fasting lipids will be evaluated only at screening. No analysis will be done for these measurements.

For urinalysis, standard dipstick measurements for specific gravity, protein, glucose, pH, blood, urine blood (non-hemolyzed), urine blood (hemolyzed), bilirubin, ketones, WBC will be done at screening. No analysis will be done for these measurements.

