For each parameter, the maximum change from baseline within each study period will be analyzed analogously.

Shift tables with respect to Common Toxicity Grade Criteria (CTC) and normal ranges will be provided. These summaries will be presented by laboratory test and treatment group. Shifts will be presented for most extreme values post-baseline.

Incidence rates of notable abnormalities will be presented ([Appendix 1](#)).

Vital signs

Analysis of the vital sign measurements using summary statistics for the change from baseline for each post-baseline visit will be performed. These descriptive summaries will be presented by vital signs and treatment group. Change from baseline will only be summarized for subjects with both baseline and post-baseline values.

All information collected will be listed by subject and abnormal values will be flagged ([Appendix 1](#)).

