16.1 Appendix 1: Clinically notable laboratory values and vital signs

The following criteria will be used to define expanded limits and notable abnormalities of key laboratory tests. Notable values for blood pressure and pulse are presented in [Table 8-4](#).

No specific action is pre-defined within this protocol to respond to specific abnormal laboratory values, as it will be decided by the investigator whether and which specific action needs to be taken to respond to any abnormal values, taking into account the overall status of the subject.

Liver Function and Related Variables

Alanine transaminase (ALT) (SGPT):	> 3 x Upper Limit of Normal (ULN)
Aspartate transaminase (AST) (SGOT):	> 3 x ULN
Total bilirubin:	> 2 x ULN
Alkaline phosphatase:	> 2.5 x ULN

Renal Function

Creatinine (serum):	> 1.5 x ULN
---------------------	-------------

[figure not shown]
Hematology Variables

Hemoglobin:	≥ 20 g/dL decrease from baseline
Platelet count:	< Lower Limit of Normal (LLN)
White blood cell count:	< 0.8 x LLN
Neutrophils:	< 0.9 x LLN
Eosinophils:	> 1.1 x ULN
Lymphocytes:	> 1.1 x ULN

Urinalysis Variable

Protein urine dipstick:	++*
-------------------------	-----

* ++ is ≥ 100 mg/dL

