3.1.1 Secondary endpoints

The study should be sufficiently powered (above 90%) to show a response rate of 46% for PASI 90 response if the placebo rate is assumed as 8%.

4 Change to protocol specified analyses

The following analyses have been removed:

- The maximum change (maximum decrease and maximum increase) from baseline within treatment period for each laboratory parameter
- The stratified Van-Eltern testing and Hodges-Lehmann estimates for the absolute value and the percentage change from baseline of DLQI total score.

5 Appendix

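### SAP 2.8.3 omits the protocol's Appendix 1 laboratory limits without declaring it, so high eosinophils and high lymphocytes have no pre-specified count

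*SAP*

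**What the plan says.** Protocol 12.6.2 (laboratory data) makes two separate commitments. The first concerns shift tables: "Shift tables with respect to Common Toxicity Grade Criteria (CTC) and normal ranges will be provided". The second concerns notable values: "Incidence rates of notable abnormalities will be presented", with a reference to Appendix 1. Appendix 1 fixes the meaning: "The following criteria will be used to define expanded limits and notable abnormalities of key laboratory tests". It lists 12 limits: five for liver and renal tests, six for hematology, and one for urine protein.

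SAP 2.8.3 begins from a different list: "The following laboratory parameters will be analyzed with respect to numerical Common Terminology Criteria for Adverse Events (CTCAE) grades". Eleven parameters follow, with cuts in Table 2-9, and Table 2-10 adds liver-related events. Eosinophils are not in Table 2-9. Lymphocytes are there only as "Lymphocyte count decreased". The same section commits to counts of newly occurring or worsening CTCAE grades, CTCAE shift tables and an exposure-adjusted incidence of neutropenia of grade 2 or higher. Normal-range shift tables are kept only as an ad hoc option.

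SAP Table 2-8 still has a column for laboratory and vital-sign notables. Table 2-11 gives the vital-sign criteria; no table gives laboratory ones. SAP section 4 lists two removals. One concerns the DLQI tests. The only laboratory item is "The maximum change (maximum decrease and maximum increase) from baseline within treatment period for each laboratory parameter".

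**The concern.** In the protocol, toxicity grading and notable values are two outputs, so CTCAE tables do not by themselves fulfil the promise on notables. A programmer working from SAP 2.8.3 would produce no table by the Appendix 1 limits, and a reader of section 4 would not learn that one had been planned.

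What is at stake is a set of protocol-specified safety counts in a placebo-controlled registration study. Two hematology abnormalities measured at every scheduled visit (protocol 8.4.1.1) would have no planned incidence by treatment group. Neutropenia, which protocol 4.5 names as an observed risk, would be counted at cuts other than the one the protocol set.

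**Working it through.** No sample size, power or alpha is involved, so there is no stated figure to reproduce. The check is a line-by-line match of Appendix 1 against SAP Tables 2-9 and 2-10.

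| Appendix 1 limit | SAP cut | Match |
|---|---|---|
| ALT > 3 × ULN | grade ≥ 2; Table 2-10 | yes |
| AST > 3 × ULN | grade ≥ 2; Table 2-10 | yes |
| Total bilirubin > 2 × ULN | Table 2-10 | yes |
| ALP > 2.5 × ULN | grade ≥ 2 | yes |
| Creatinine > 1.5 × ULN | grade ≥ 2 | yes |
| Platelets < LLN | grade ≥ 1 | yes |
| Neutrophils < 0.9 × LLN | grade 1 from LLN, grade 2 below 1.5 | different cut |
| WBC < 0.8 × LLN | grade 1 from LLN, grade 2 below 3.0 | different cut |
| Eosinophils > 1.1 × ULN | none; eosinophilia occurs only within a liver composite | no count |
| Lymphocytes > 1.1 × ULN | low side only | no count |
| Hemoglobin fall from baseline | absolute level only | different quantity |
| Urine protein ++ | urinalysis at screening only, not analysed | no count |

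Totals: 6 match + 2 different cut + 2 high-side hematology limits without a count + hemoglobin + urine protein = 12.

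**Neutrophils.** The SAP's grade 1 band is "<LLN - 1.5 x 10e9 /L". Because 0.9 × LLN is always below LLN, every Appendix 1 value is grade 1 or higher, but the Appendix 1 cut never equals the grade ≥ 1 cut. It equals the grade ≥ 2 cut when 0.9 × LLN = 1.5, so LLN = 1.5 / 0.9 = 1.667.

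**WBC.** The grade 1 band is "<LLN - 3.0 x 10e9 /L". By the same reasoning, equality with grade ≥ 2 needs 0.8 × LLN = 3.0, so LLN = 3.0 / 0.8 = 3.75.

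Protocol 8.4.1 leaves reference ranges to the laboratory manual, so the LLN values below are assumptions (× 10⁹/L).

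| Assumed neutrophil LLN | 0.9 × LLN | Against grade ≥ 2 (< 1.5) |
|---|---|---|
| 1.5 | 1.35 | stricter |
| 1.8 | 1.62 | looser |
| 2.0 | 1.80 | looser |
| 2.2 | 1.98 | looser |

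| Assumed WBC LLN | 0.8 × LLN | Against grade ≥ 2 (< 3.0) |
|---|---|---|
| 3.0 | 2.4 | stricter |
| 3.5 | 2.8 | stricter |
| 4.0 | 3.2 | looser |
| 4.5 | 3.6 | looser |

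So the direction of the difference depends on the laboratory. With a neutrophil LLN of 1.8 to 2.0, values from 1.5 up to 1.62–1.80 are notable under the protocol but fall outside the SAP's exposure-adjusted neutropenia rate. In that situation a subject who is grade 1 at baseline and then drops below 0.9 × LLN while staying in grade 1 is neither new nor worsening under the SAP count.

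**Hemoglobin.** Appendix 1 asks for a fall of at least 20 g/dL. In the units of SAP Table 2-9 that is 20 × 10 = 200 g/L, more than the whole of any baseline below 200 g/L. The entry needs checking before it is programmed.

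**The case against.** The best defence is that nothing has been replaced. Toxicity grading was already in the protocol, the SAP offers no rival definition of a notable laboratory value, Table 2-8 keeps a column for laboratory notables, and SAP section 1 says the data are analysed according to protocol section 12, which invokes Appendix 1. The SAP also relies on a master analysis plan and table shells that are not among the documents, and the cells of Table 2-8 are partly broken in the extracted text.

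This stands in part. A reader might infer that the SAP redefines laboratory notables as CTCAE grades; the documents show only an undefined term and an undeclared omission. A general pointer does not repair that, because section 4 is where departures are listed and 2.8.3 is where criteria would be expected. For vital signs the SAP does restate the protocol's limits.

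A reader might also infer that high eosinophils and lymphocytes could never surface. That goes too far. All laboratory data are listed and out-of-range values flagged. Change from baseline is summarised at each visit, with quartiles and extremes. Clinically significant values are reported as adverse events (protocol 10.1.1). The optional shift tables, if run, would count values above ULN, though not above 1.1 × ULN. What is missing is a committed count.

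Nor is neutropenia left unanalysed: every value under the Appendix 1 neutrophil or WBC cut still receives a CTCAE grade. Finally, the endpoint attached to the safety objective in protocol Table 2-1 is change from baseline in laboratory variables together with adverse events, and the SAP delivers both. The notable-value incidence is an additional protocol commitment, not that endpoint.

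**Conclusion.** The point holds as an undeclared omission. Following SAP 2.8.3 as written drops a protocol-specified descriptive output. Eosinophils and lymphocytes above 1.1 × ULN lose any pre-specified count. Neutrophils and WBC remain captured within grade ≥ 1, but at cuts that differ from Appendix 1 and coincide with grade ≥ 2 only at the two LLN values derived above. The hemoglobin fall and urine protein are also left without a count or a declaration. The other six limits are already served by matching cuts.

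The co-primary tests, the key secondary test, alpha and sample size are untouched. The match itself needs no assumption; only the size and direction of the neutrophil and WBC differences rest on assumed LLNs. If the unseen table shells already contain an Appendix 1 table, the gap is one of documentation, and it should still be closed in the SAP.

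**What to change.** 1. In SAP 2.8.3 add one table of newly occurring Appendix 1 notable values, by period and treatment group, for eosinophils > 1.1 × ULN, lymphocytes > 1.1 × ULN, neutrophils < 0.9 × LLN and WBC < 0.8 × LLN. Point the laboratory part of the notables column in Table 2-8 to it.
2. In SAP section 4 state that ALT, AST, ALP, bilirubin, creatinine and platelets are covered by Tables 2-9 and 2-10; that urine protein is not analysed because urinalysis is done at screening only; and that normal-range shift tables are now optional.
3. For hemoglobin, either add the decrease-from-baseline criterion once the Appendix 1 entry has been checked, or declare it removed. It should not be described as covered by Table 2-9, which grades the absolute level.

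The cost is one table from data already collected (a hemoglobin row is optional) and a few lines of SAP text. No new assessments are needed.

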2.1.1.3 Screening, baseline and post-baseline definitions

Screening refers to any procedures (e.g., checking inclusion and exclusion criteria) performed prior to the date of first dose of study treatment (for safety analysis) or prior to the randomization date (for efficacy analysis). Per protocol, subject informed consent must be obtained prior to performing any study related activity. The date of signing informed consent is the start date of screening period. Any assessment obtained during the screening period will be labeled screening assessment. Assessments made on Day 1 may occur before or after the randomization or the first dose. Further information will be found in [\[Programming Datasets Specifications \(PDS\)\]](#).

For efficacy analyses, baseline is the last assessment (including unscheduled visits) obtained (on or) before the randomization (day). All assessments obtained after randomization are considered as post-baseline unless otherwise specified.

For safety analyses, baseline is the last assessment (including unscheduled visits) obtained (on or) before the first dose (day) of study treatment. All assessments obtained after the first dose (day) of study treatment are considered as post-baseline unless otherwise specified.

Of note, baseline will be derived based on the randomization day or first dose day, exact randomization/dosing time is not considered.

Of note, re-randomization will not be used for baseline definition and only one baseline value will be defined referring to the first randomization.

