2.8 Safety analyses

All safety analyses will be based on the safety set. Only those scheduled visits which were pre-planned in the protocol will be reported in tables and figures for safety variables.

Treatment groups for evaluation of entire treatment

The summaries of evaluation will be reported for treatment period 1 and entire treatment period, respectively. Week 16 primary analysis will include data up to Week 12 for treatment period 1 and data up to Week 16 last patient last visit (LPLV) for the entire treatment period.

The following groups will be used for treatment period 1:

- **AIN457 300 mg (2mL AI)**: all subjects who are randomized to 300 mg 2mL AI group at Randomization visit
- **AIN457 300 mg (2x1mL PFS)**: all subjects who are randomized to 300 mg 2x1mL PFS group at Randomization visit
- **Placebo**: all subjects who are randomized to a placebo group at Randomization visit
- **Any AIN457 300 mg**: Any AIN457 300 mg of (2mL AI) or (2x1mL PFS) as above.

The following groups will be used for entire treatment period:

- **AIN457 300 mg (2mL AI)**: all subjects who are randomized to 300 mg 2mL AI group at Randomization visit
- **AIN457 300 mg (2x1mL PFS)**: all subjects who are randomized to 300 mg 2x1mL PFS group at Randomization visit
- **Any AIN457 300 mg (2mL AI)**: all subjects who are randomized to 300 mg 2mL AI group at Randomization visit and all placebo subjects who are re-assigned to 300 mg 2mL AI at Week 12, but they are only considered after the treatment re-assignment (Week 12 treatment injection).
- **Any AIN457 300 mg (2x1mL PFS)**: all subjects who are randomized to 300 mg 2x1mL PFS group at Randomization visit and all placebo subjects who are re-assigned to 300 mg 2x1mL PFS at Week 12, but they are only considered after the treatment re-assignment (Week 12 treatment injection).
- **Any AIN457 300 mg**: Any AIN457 300 mg of (2mL AI) or (2x1mL PFS) as above.
- **Placebo**: all subjects who are re-assigned will only be considered until the re-assignment point (Week 12 treatment injection).

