2.8.4.2 Vital signs

Analysis in vital sign measurement using descriptive summary statistics for the change from baseline for each post-baseline visit will be performed by vital sign and treatment group. Change from baseline will only be summarized for subjects with both baseline and post-baseline values and will be calculated as:

$$\text{change from baseline} = \text{post-baseline value} - \text{baseline value}$$

Only “on-treatment” vital signs will be summarized (i.e. assessments within last dose plus 84 days). All vital signs will be listed with “on-treatment” flag displayed.

The number and percentage of subjects with newly occurring notable vital signs abnormalities will be presented. Criteria for notable vital sign abnormalities are provided in [Table 2-11](#) below. A listing of subjects with newly occurring notably abnormal vital signs will be provided.

Table 2-11 Criteria for notable vital sign abnormalities

Vital sign (unit)	Notable abnormalities
Systolic blood pressure (mmHg)	$\geq 140 \text{ mmHg}$ or $< 90 \text{ mmHg}$
Diastolic blood pressure (mmHg)	$>90 \text{ mmHg}$ or $<60 \text{ mmHg}$
Pulse (bpm)	$> 100 \text{ bpm}$ or $<60 \text{ bpm}$

[REDACTED]

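### In the pooled Any AIN457 safety columns, switched placebo subjects are counted from Week 12 but keep a Day 1 baseline, so an abnormality that arose on placebo and persists is scored as new on secukinumab

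*SAP*

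**What the plan says.** SAP 2.1.1.3 gives the general safety rule: "For safety analyses, baseline is the last assessment (including unscheduled visits) obtained (on or) before the first dose (day) of study treatment". It adds that "only one baseline value will be defined referring to the first randomization". SAP 2.8.3 repeats the rule for the CTCAE shift tables: "baseline will be defined as last assessment prior to first dosing in initial treatment phase".

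SAP 2.8 defines the reporting columns. "The summaries of evaluation will be reported for treatment period 1 and entire treatment period, respectively". In the entire-period tables, Any AIN457 300 mg (2mL AI) includes "all placebo subjects who are re-assigned to 300 mg 2mL AI at Week 12". The time counted for them is then limited by the words "but they are only considered after the treatment re-assignment (Week 12 treatment injection"). The PFS column has a parallel rule, and both feed Any AIN457 300 mg. The placebo column follows re-assigned subjects only up to the same injection.

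The outputs that depend on baseline are these:

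- SAP 2.8.3: "The number and percentage of subjects with CTCAE grade newly occurring or worsening after baseline will be presented". The section also has CTCAE shift tables, exposure-adjusted incidence of newly occurring neutropenia of grade 2 or higher, newly occurring liver abnormalities, and by-visit change from baseline.
- SAP 2.8.4.2: "The number and percentage of subjects with newly occurring notable vital signs abnormalities will be presented", together with by-visit change from baseline.

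Neither document sets a Week 12 baseline for switchers, and neither removes abnormalities already present before the switch.

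**The concern.** The two rules do not fit together. For a switched subject, the time at risk in the Any AIN457 columns starts at the Week 12 injection. The value that decides whether a finding is new was taken before 12 weeks of placebo. Whatever changed during those 12 weeks and is still visible afterwards falls to secukinumab in the table. The same subject may already have been counted as new in the placebo column, so one finding can appear under both treatments.

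By-visit change from baseline has a related problem: a switcher's change combines drift on placebo with the effect of secukinumab.

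The Any columns are the largest secukinumab safety groups in a trial meant to support registration of the 2 mL auto-injector. They also appear in the Week 16 analysis, which Protocol 4.4 intends for submission. With groups of this size, one or two miscounted subjects visibly change a percentage.

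**Working it through.** The plan gives no figure for this point. Its only design figures are the power statements with 40 per group. These reproduce by exact enumeration of Fisher's test at one-sided 2.5%: 99.97% for PASI 75, 99.7% for IGA 0 or 1 and 97.3% for PASI 90. They do not enter what follows.

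**Step 1. How the rules classify a switched subject**

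| Day 1 | Week 12, pre-dose | After Week 12 injection | Day 1 baseline (SAP) | Week 12 baseline |
|---|---|---|---|---|
| normal | abnormal | still abnormal | new on secukinumab | not new |
| abnormal | normal | abnormal again | not new | new on secukinumab |
| normal | normal (abnormal at Week 8 only) | normal | not counted | not counted |
| normal | grade 1 | grade 2 | new or worse | worse |
| normal | normal | abnormal | new | new |

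The first two rows differ, in opposite directions. The third shows that a placebo-period change that resolved before the switch and did not return adds nothing.

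**Step 2. How many subjects are exposed**

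Inputs:
- About 120 subjects at 2:2:1:1 (SAP 1.1), so 40 AI, 40 PFS and 20 + 20 placebo.
- Placebo PASI 90 non-responders switch at Week 12 (SAP 1.1).
- Assumed placebo PASI 90 rate of 8% (SAP 3.1.1).
- No dropout (my simplification).

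Results:
- Switchers: 40 × (1 − 0.08) = 36.8.
- Any AIN457 300 mg: 80 + 36.8 = 116.8. Share: 36.8 / 116.8 = 31.5%.
- Each device column: 18.4 / (40 + 18.4) = 31.5%.
- If no placebo subject reached PASI 90: 40 / 120 = 33.3%.

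**Step 3. Possible size of the miscount**

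Let q be the share of switchers whose abnormality arose on placebo, is seen after the Week 12 injection, and would not be new or worse against the Week 12 value. The documents give no q; the range is an assumption.

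- Miscounted subjects = 36.8 × q.
- Percentage points = 100 × 36.8 × q / 116.8.
- Person-years = 80 × 1 + 36.8 × 40/52 = 108.3, taking 52 weeks for randomized secukinumab subjects and 40 weeks for switchers.

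| q (assumed) | Subjects | Percentage points | Per 100 person-years |
|---|---|---|---|
| 1% | 0.4 | 0.3 | 0.3 |
| 2% | 0.7 | 0.6 | 0.7 |
| 5% | 1.8 | 1.6 | 1.7 |
| 10% | 3.7 | 3.2 | 3.4 |

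In the Any 2 mL AI column a single case adds 1 / 58.4 = 1.7 percentage points. These are gross figures, not reduced by the opposite error in row 2 of the first table. With a pre-switch baseline the miscount is zero by construction.

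**Step 4. Are the data available?**

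Hematology and chemistry are measured at all scheduled visits (Protocol 8.4.1.1 and 8.4.1.2) and vital signs at every scheduled visit (Protocol Table 8-4). Safety assessments precede dosing (Protocol 8 and 8.4). A Week 12 pre-injection value is therefore already planned.

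**The case against.** A reader might infer that the trial cannot answer its safety objective. The documents do not support that. The objective is safety compared with placebo, and Treatment Period 1 gives that comparison between randomized groups with Day 1 as the right baseline for everyone. The entire-period tables also keep separate columns for subjects originally randomized to AI or PFS, which contain no switchers. No text says registration rests on the Any columns.

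A reader might also infer that every placebo-period change is charged to secukinumab. Only those seen after the Week 12 injection can be. Nor do the documents support any particular rate of miscounting; one rate for pulse and for liver enzymes alike is only an illustration.

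Other points that stand:
- For liver and vital-sign criteria the SAP does not define newly occurring separately. Reading it against the single baseline is an inference, though SAP 2.1.1.3 leaves no other. The SAP also refers to a master analysis plan and dataset specifications that cannot be seen here.
- The opposite error is partly a matter of definition, since an abnormality present before any study drug can fairly be called pre-existing. For grade 2 neutropenia it is largely ruled out, because neutrophils below 1,500/µL at Screening exclude a subject.
- Abnormal cases are listed individually, and listings are by treatment sequence, so a careful reader can trace when a finding arose. That does not correct the tables.
- Carried-over cases inflate secukinumab incidence, which is conservative for a safety claim. The opposite error is not conservative.
- Changing the baseline alone would damage the by-visit tables. Four weeks on drug for a switcher at Week 16 would be pooled with 16 weeks for a randomized subject.

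**Conclusion.** The concern holds for the entire-period Any AIN457 columns. The single Day 1 baseline and the Week 12 start of counting are both explicit, and together they misattribute abnormalities that arose on placebo and persist after the switch. They also miss some that return on secukinumab. About 37 of 117 subjects are exposed at the planned 8% placebo PASI 90 rate, assuming no dropout. How many would actually be miscounted is unknown; the 0.4 to 3.7 subjects shown rest entirely on the assumed 1% to 10%. The reading is firmest for the CTCAE tables, where the baseline is stated, and slightly less firm for liver and vital-sign criteria.

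The point concerns descriptive pooled safety tables. The Treatment Period 1 comparison, the originally randomized secukinumab columns, and the efficacy tests, alpha and power do not change. It should still be corrected, because the remedy is cheap and the data are already collected.

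**What to change.** Amend SAP 2.1.1.3, 2.8.3 and 2.8.4.2 as follows, for re-assigned placebo subjects in the Any AIN457 columns only.

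1. Define safety baseline as the last value before the Week 12 active injection.
2. Use it for the CTCAE shift and new-or-worsening tables, exposure-adjusted neutropenia, newly occurring liver criteria and newly occurring notable vital signs.
3. State that newly occurring in the liver and vital-sign tables is relative to this baseline.
4. Keep the Day 1 baseline for the placebo column and for subjects originally randomized to secukinumab.
5. For by-visit change from baseline, either show switchers separately or, if the new baseline is used, count their visits from the Week 12 injection. Protocol 12 already lists the two placebo-switched groups for the entire study, so separate display needs no new grouping.

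The cost is SAP wording, a second baseline flag in the laboratory and vital-sign datasets, and a table footnote, plus re-timed visits if that option is chosen. No new data are needed. The drawback is that each switcher has two baselines, and the footnote must say which one each column uses.
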